### c. Non-standard software to be provisioned to vDI

Please provide specific details below. Note: Applicant is responsible for contracting and licensing software from vendor or OptumLabs if available.

No non-standard software will be needed.

Software (Name/Manufacturer)	Version #	Name/Email of install contact
Not applicable.		

### 7. Special Project Related Approvals

### a. IRB Approval

Will this project require IRB approval from your institution? No, please see below for details. If yes, please estimate duration required for IRB approval (if known)

At Brown University, projects like this require consultation with the IRB and an attestation by the Principal Investigator that the data are de-identified. Once this is provided, the IRB furnishes a formal letter waiving the need for further review. In that last three projects led by [name], including one that used OptumLabs data, this process has taken less than 2 weeks to complete.

### b. Publication Approval

Does any party outside your institution have rights to review, approve, or control dissemination of the reports of this project? Please explain.

## No outside part has rights to review, approve, or control dissemination of the reports of this project.

### c. External Data Approval

Will this project include any external data being brought into the project sandbox, beyond simple code lists?

### No.

If yes, this file will need to be reviewed and approved for compliance by OptumLabs. Has this file been reviewed and approved?

### Not applicable.

A description of the file will be needed for the project SOW.

Not applicable.

### 8. Services Requested from OptumLabs

### a. Staff Services from OptumLabs

None requested.

Resource Type	Deliverables	Estimated hours	Estimated service dates
Not applicable.			

### b. Other Services from OptumLabs

None requested.

Service Description*	Date needed	Comments
Not applicable.		

### 9. Analysis Plan

#### a. Methods

A note on the choice of analysis methods: For analysis results to have a tenable interpretation, it is important that the analysis methods be appropriate for the target causal parameters of interest. Thus, when comparing estimates from a collection of specific statistical methods, care is needed to ensure that all the methods under consideration can be used to estimate the same causal parameter (and that they can do so under compatible causal assumptions). Consider two concrete examples of direct relevance to this proposal: (1): single equation, multivariable single equation regression methods (i.e., maximum likelihood estimation of the coefficients of a multi-variable regression) estimate conditional average treatment effects (conditional on all the covariates entered in the regression together with the treatment indicators). For non-linear regression models (including the popular logistic regression and Cox proportional hazards regression models) these conditional average treatment effects are not in general equal to the corresponding population-averaged (marginal) causal effects. For instance, the coefficient from a multivariable logistic regression model of the outcome on treatment and covariates does not equal to the marginal odds ratio, even if the multivariable regression model is correctly specified and in the absence of any unmeasured confounding (this phenomenon relates to the non-collapsibility of the odds ratio; in general the conditional odds ratio is expected to be further away from the null compared to the marginal odds ratio, except in rare cases). (2) Inverse probability weighting, matching, and instrumental variable estimators do not estimate the same population-averaged causal effects: Specifically, *inverse probability weighing* targets the average treatment effect in the entire population (or the average treatment effect in the treated/controls, with appropriate choice of odds weights). Matching methods estimate causal effects in populations that depend on the data generating mechanism and the matching algorithm (e.g., 1-to-1 matching without replacement, when one treatment is much less commonly prescribed than the comparator produces estimates of the average treatment effect in the population treated with the rarely prescribed treatment). Lastly, instrumental variable methods estimate different causal parameters depending on auxiliary assumptions that are untestable; under homogeneity, they estimate the average treatment effect; under certain structural nested mean models

assumptions, they estimate the average treatment effect on the treated; and under monitonicity, the estimate the so-called average treatment effect on the compliers.\*

Choice of causal models and methods of estimation for the current project: With the above point in mind, in Table 3, we have identified target parameters that are of scientific and policy interest for the ROCKET trial and the LEAD-2 trial emulations (the same methods would apply to the corresponding "expanded population" analyses). The target parameters we have listed are identifiable under randomization (in the actual trials) and thus are natural choices for the emulation analyses. For each of these target parameters we have described *causal* (counterfactual) models under which the identification of the same target parameters can be considered when using observational data (in the emulations and the expanded population analyses). Last, for each target parameter - causal model combination we have listed our choice of estimation methods. It is not feasible to give complete details for the implementation of each of these analysis methods within the scope of the current proposal (full details will be provided in the study protocol to be generated is this proposal is selected for funding). Instead, we have provide here a number of citations to technical papers or book chapters that describe the implementation of the method in the table (we have intentionally focused on works by [name] and collaborators to establish that we have the capability to implement the methods for the project's purposes). We now discuss aspects of the analyses that are cross-cutting, in the sense that they can influence the results of many of the listed techniques.

Censoring- and adherence-adjusted analyses: These two types of analyses, though different in their goals, are closely related because they involve the estimation of treatment effects of time-varying interventions (to prevent censoring over time; or to enforce a particular adherence level). For these analyses we expect to work in discrete time (we expect that 1 month intervals will be feasible and give a reasonable approximation to the underlying continuous functions) and define variables that capture treatment status based on prescribing information (e.g., prescriptions filled, number of pills). The discrete time structure is reasonable for claims data and allows for practical ways of collecting information on time-varying exposures and treatments. Note that the discrete time structure allows the computation of functions of cumulative exposure that can be made arbitrarily flexible and thus can (in theory) approximate the true cumulative exposure-outcome function, while properly adjusting for time varying covariates. We note that popular adherence measures such as medication possession ratios. when entered in conditional outcome models or models for the propensity score produce invalid results in the presence of time-varying confounding (except under highly implausible assumptions). In adherence-adjusted analyses, we will use clinically meaningful definitions of adherence. Specifically, individuals who discontinue treatment due to toxicity or other clinically mandated reasons will be considered to be adhering to the emulated trial protocol, as no reasonable protocol would force patients to stay on treatment in these situations. For censoring due to death, we will use the suggestions by Young et al. to conceptualize the target parameters and refine our analysis choices.

Modeling and robustness to model misspecification: In addition to the causal models described in **Table 3**, our analytical methods require the specification of working models for a number of regression functions (conditional probability or expectation functions), such as

<sup>\* The difficulties with instrumental variables outlined here, together with our belief that useful and valid instrumental variables are exceedingly hard to find in routinely collected claims or EHR data, are the reason why we decided not to include instrumental variable methods in this proposal.

models for the probability of treatment, the outcome, censoring, and treatment adherence over time. Our main analyses will use *parametric working models* because they are the most commonly used approach in practice and because in our experience – if made sufficiently flexible – they approximate the results of semiparametric or nonparametric models fairly closely. As a stability analysis, we will repeat our analyses using semi-parametric methods to estimate the working models. Specifically, we will use random forest methods (when modeling discrete responses), and lasso or elastic-net regularized generalized linear models (for both binary and continuous responses). Because we plan to work in discrete time for survival analyses, and in censoring- and non-adherence adjusted analyses, the corresponding models will be pooled (over time periods) generalized linear models for binary responses.

When using parametric models, our initial modeling strategy *will be to enter all variables deemed likely confounders in the models on the basis of substantive knowledge*, with flexible terms for continuous variables (restricted cubic splines with 5 knots at the default positions) and product terms between variables when indicated by substantive knowledge or model specification assessments (e.g., covariate balance after inverse probability weighting or after propensity score matching). Note that in the stability analyses using semi-parametric models sparsity-appropriate model selection is built into our chosen procedures.

We will model time nonparametrically (e.g., with appropriate indicator variables in discrete time), as needed (e.g., in survival analyses or adherence- and censoring-adjusted analyses). When nonparametric modeling of time is not possible (e.g., due to rare events) we will begin by using restricted cubic splines with 7 knots and then progressively reduce the number of knots until the models can be estimated.

Whenever the data allow, we will not make homogeneity assumptions among treatment groups (e.g., outcome regression models and probability of censoring models will be fit separately by treatment group).

To reduce the impact of possible model misspecification, when available, we have chosen to include multiply robust estimators (both estimating equation- and TMLE-based) in our analysis plan (Table 3). These estimators utilize multiple working models and remain consistent and asymptotically normal when either model (but not necessarily both) is correctly specified. For technical reasons that are beyond the scope of this proposal, we will only use semi-parametric methods to estimate working models in combination with doubly robust estimators.

**Table 3:** Target parameters, measures of treatment effect, causal models, and methods of estimation.

Target	Measure of effect	Causal models; methods of estimation	Notes about additional assumptions or special issues in				
parameter			estimation				
ROCKET TRIAL (failure time outcome)							
Intention-to-treat conditional treatment effect	Conditional hazard ratio (averaged over the follow-up period if the conditional counterfactual hazards are not proportional)	
 
Multivariable adjusted Cox regression model; maximum partial likelihood
 
	These approaches correspond to the "single equation method" asked for in the RFP. Note that marginalizing the estimated Cox model over the baseline covariates is equivalent to approach (2) below, except for the assumption of conditional proportional hazards.				
Intention-to-treat effect in the total population of eligible individuals (unadjusted for non-adherence)	Marginal difference of survival probabilities as specified time points & survival curves for each treatment	
 
(2) g-formula computation; outcome model-based standardization following outcome regression
 
(3) Marginal structural survival probability model with time-varying marginal counterfactual hazards; inverse probability of treatment weighting
 
(4) Efficient and doubly robust estimation using estimating equations
 
(5) Efficient and doubly robust estimation using TMLE
 
	All approaches listed here do not require proportional hazards assumptions over the treatment indicator. Approach (2) adjusts both for confounding and censoring. Approaches (3) through (5) require combination with inverse probability of censoring weighting to adjust for censoring. We will perform both censoring adjusted and unadjusted analyses. Approaches (4) and (5) are based on the efficient influence function and are locally efficient and doubly robust.				
	Marginal survival ratio comparing treatments & marginal hazard ratio (using a Weibull distribution)	(6) Nested structural accelerated failure time model; g- estimation	When using a Weibull parametric family, we can recover a hazard ratio from the accelerated failure time model, using the dual interpretation of Weibull regression as a proportional hazards and accelerated failure time model.				
	Marginal hazard ratio (averaged over the follow-up period if the marginal counterfactual hazards are not proportional)	(7) Marginal structural Cox proportional hazards model; inverse probability of treatment weighting	Assumes proportional marginal counterfactual hazards among treatment groups.				
Intention-to-treat effect in the treated (unadjusted for non-adherence)	Marginal difference of survival probabilities as specified time points & survival curves for each treatment	
 
(8) Matching on the estimated probability of treatment, followed by non-parametric modeling of the survival probability as a function of time, in each treatment group
 
(9) Marginal structural survival probability model with time-varying marginal counterfactual hazards (in the total study sample); inverse odds of treatment weighting
 
(10) Matching followed by Cox propertional bazards
 
	Using indicator functions for time-periods and interactions with treatment group this approach avoids proportional hazards assumptions. Naïve nonparametric bootstrap inference is not appropriate for some matching estimators because they are non-smooth (see the text of the proposal for how we intend to address this).				
	iviarginal nazaro ratio	(10) matching followed by Cox proportional nazards	Same as above.				

	(averaged over the follow-up period)	regression (11) Marginal structural Cox proportional hazards model; inverse probability of treatment weighting					
Per-protocol effects (i.e., adjusted for non- adherence)	Marginal difference of survival probabilities as specified time points	
 
(12) g-formula computation; outcome model-based standardization following nested regression
 
(13) Marginal structural model with time-varying hazard; inverse probability of treatment weighting
 
(14) g-estimation of accelerated failure time model
 
	These methods can account for observed non-adherence and estimate the effects of complete adherence or partial adherence.				
LEAD-2 trial (continuous outcome evaluated at the end of the study)							
Intention-to-treat conditional treatment effect	Conditional mean difference ratio	(15) Multivariable conditional outcome model; adjusted ordinary least squares regression	These approaches correspond to the "single equation method" asked for in the RFP. Note that marginalizing over the baseline covariates is equivalent to approach (13) below.				
Intention-to-treat effect in the total population of eligible individuals (i.e., unadjusted for non-adherence)	Marginal mean difference at the end of the study	
 
(16) g-formula computation; outcome model-based standardization following outcome regression
 
(17) Marginal structural mean model; inverse probability of treatment weighting
 
(18) Efficient and doubly robust estimation using estimating equations
 
(19) Efficient and doubly robust estimation using TMLE
 
(20) Nested structural mean model; g-estimation
 
	Approach (16) also addresses early dropout from the study. Approach (17) needs to be combined with inverse probability of outcome missingness (i.e., no early drop-out) to account for individuals who do not have measurements at the end of the study. Inverse probability of outcome missingness weights can also be used with approaches (18) through (20).				
Intention-to-treat effect in the treated (i.e., unadjusted for non-adherence)	Marginal mean difference at the end of the study	
 
(21) Matching on the estimated probability of treatment
 
(i.e., the propensity score)
 
(22) Marginal structural mean model (in the total study sample); inverse odds of treatment weighting
 
	Using indicator functions for time-periods and interactions with treatment group this approach avoids proportional hazards assumptions. Naïve nonparametric bootstrap inference is not appropriate for some matching estimators because they are non-smooth (see the text of the proposal for how we intend to address this).				
Per-protocol effects (i.e., adjusted for non- adherence)	Marginal mean difference at the end of the study	
 
(23) g-formula computation; outcome model-based standardization following nested regression
 
(24) Marginal structural mean model for time-varying treatments; inverse probability of treatment weighting
 
(25) Nested structural mean model for time-varying treatments; g-estimation
 
	These methods can account for observed non-adherence and estimate the effects of complete adherence or partial adherence.				

RFP = request for proposals; TMLE = targeted minimum loss estimation.

**Dealing with extreme weights in weighted analyses:** Many of the estimation approaches we propose to use involve the estimation of inverse probability weights (for treatment initiation, censoring, or non-adherence). These estimation approaches are sensitive to near-violations and violations of related positivity assumptions (i.e., the assumptions of positive probability of treatment assignment, of no-censoring, and of full adherence). We will address issues related to extreme weights using an explicit bias-variance tradeoff framework. After estimating the weights, and before estimating treatment effects, we will begin by finetuning our selection criteria and examining the covariates that may be responsible for the extreme weights. If difficulties persist, we will repeat our analyses after trimming or truncating extreme weights using from the 99th to the 95th percentile of the weight distribution to define "extreme" weights.

**Matching estimators:** We have noted above the difficulties when comparing the results from matching estimators against other methods of estimation for population-averaged causal effects (e.g., IP weighting). In the table, we have listed matching as estimating the average treatment effect on the treated because our background knowledge and the preliminary counts reported in **Section 11b** suggest that the treatment group corresponding to the "experimental intervention" in the emulated trial will be less common than the treatment group corresponding to the "control intervention"; in such cases, matching methods (unless combined with additional weighting) approximately estimate the average treatment effect in the population of patients treated with the experimental intervention (i.e., the average treatment effect on the treated). We will use 1-to-many matching on the propensity score with replacement, within calipers of 0.1 standard deviation (on the logit-propensity score scale). Because matching estimators are non-smooth we will consider to use of the m-out-of-n bootstrap and the methods described by Otsu et al. to improve the performance of bootstrap methods ([name] is currently supervising a PhD student, not budget for in this proposal, who has already implemented methods to address these very issues).

**Issues of statistical inference and bootstrap methods:** In general, our preference will be to provide inference (statistical tests and 95% confidence intervals) via the non-parametric bootstrap. Specifically, we will (1) sample the observed study data on covariates, treatments, and outcomes with replacement; (2) repeatedly perform the desired analyses collecting the results; and (3) examine the bootstrap distribution and use it for inference. In most cases and in large samples, we have found that the percentile bootstrap intervals and the normal-approximation Wald-style bootstrap intervals work reasonably well for the proposed statistical methods (and produce similar results). We will address any issues by using bootstrap variants that have better performance than the standard non-parametric bootstrap in challenging cases (e.g., as described for non-smooth matching estimators, described above). We will use the bootstrap results for inference on the counterfactual survival probabilities (in the ROCKET trial emulation), counterfactual outcome means (in the LEAD-2 trial emulation), and the treatment effect measures listed in **Table 3**.

Missing covariate and outcome data: We do not expect substantial covariate missingness in the claims data. Outcome missingness in claims analyses will be addressed by the censoring-adjusted analyses described above. We expect much greater outcome missingness when using laboratory results (linked to the claims or from the EHR), and also that HbA1c values will be obtainable from 2 separate sources (laboratory results linked with the claims data or via the EHR linkage to be performed for this project). Furthermore, when using laboratory results as regressors in working models, regardless of the data source, baseline and time-varying covariate missingness is likely to be a major issue in the both trial emulations. Our main analysis will use complete cases, in order to avoid the need for additional modeling assumptions

(e.g., when modeling the missing data conditional on the observed data under missing at random assumptions). As a stability analysis, we will repeat our analyses using multivariate normal multiple imputation. In our prior OptumLabs work, we have found that multivariate normal multiple imputation performed well in this setting and returned results similar to multiple imputation using chained equations. To combine multiple imputation with the bootstrap we will use the approach suggested by Schomaker & Heumann.

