### Comparisons between the observational analysis results and the target trial, and

**comparisons among different estimators:** We will use the bootstrap results described above to compare treatment effect estimates from the observational analyses against the published randomized trial results. As suggested in the RFP, we will use the following criteria to organize our comparisons: (1) regulatory agreement, defined as statistically significant result with directional equivalence between the RCT and observational study; and (2) estimate agreement, defined as the point estimate of the observational study falling within the 95% confidence interval of the ATE from the RCT using the reported standard errors of the RCT to define the confidence interval. We also believe that the following additional comparison may be useful: (3) estimate the point estimate and confidence interval for the ratio or difference of the trial estimate vs. the corresponding observational study estimate (the choice between taking the difference of the estimators or their ratio will be based on whether the effect measure is additive or multiplicative, respectively).

Last, we will use the bootstrap results to compare the treatment effect estimators listed in **Table 3** when appropriate, that is, when the estimators share the same target parameter

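### Table 3 approach (11) is listed as a hazard ratio in the treated, but its weights give the total-population hazard ratio already produced by approach (7)

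*Protocol*

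**What the plan says.** Table 3 in section 9.a of the Protocol groups the ROCKET estimators by target parameter.

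- **Total-population block**, headed "Intention-to-treat effect in the total population of eligible individuals (unadjusted for non-adherence". Its marginal hazard ratio is approach "7) Marginal structural Cox proportional hazards model; inverse probability of treatment weighting".
- **Treated block**, headed "Intention-to-treat effect in the treated (unadjusted for non-adherence". Its marginal hazard ratio has two approaches: (10), matching followed by Cox regression, and "11) Marginal structural Cox proportional hazards model; inverse probability of treatment weighting".
- **Other weighted entries for the effect in the treated.** Approach (9), for ROCKET survival differences, is specified "in the total study sample); inverse odds of treatment weighting". The LEAD-2 entry is "22) Marginal structural mean model (in the total study sample); inverse odds of treatment weighting".

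The note on the choice of methods that opens section 9.a says that inverse probability weighting "targets the average treatment effect in the entire population (or the average treatment effect in the treated/controls, with appropriate choice of odds weights". The paragraph on matching estimators lists matching as approximating the effect in the treated, because the experimental drug is expected to be the less common one. The paragraph on comparisons says bootstrap comparisons among Table 3 estimators will be made "when appropriate, that is, when the estimators share the same target parameter".

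**The concern.** One procedure cannot be the stated estimator of two different target parameters. Apart from their numbers, (7) and (11) carry the same method, yet one sits under the total population and the other under the treated. By the Protocol's own account, the weights named in (11) belong to the first block.

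This matters more here than in most plans, because comparing estimators is the product of the project. Table 3 tells the analyst which estimators share a target and may be compared. It would pair (10) with (11), so a difference in target population could be reported as a difference between matching and weighting. The ROCKET hazard ratio in the treated would have no weighting-based counterpart to matching. Approach (11) would add nothing to (7) while appearing as a separate result.

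**Working it through.** **The text, row by row**

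| Approach | Block | Measure | Weights named |
|---|---|---|---|
| (7) | Total population, ROCKET | Hazard ratio | Inverse probability |
| (9) | Treated, ROCKET | Survival difference | Inverse odds |
| (11) | Treated, ROCKET | Hazard ratio | Inverse probability |
| (22) | Treated, LEAD-2 | Mean difference | Inverse odds |

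Of the three weighted entries in the treated blocks, only (11) names inverse probability weights. It also lacks the remark about the total study sample that (9) and (22) carry.

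**What each set of weights targets**

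Let p be the probability of rivaroxaban given baseline covariates. At a given covariate value, a fraction p receive rivaroxaban and 1 − p receive warfarin.

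- Inverse probability weights, 1/p and 1/(1 − p): rivaroxaban p × 1/p = 1; warfarin (1 − p) × 1/(1 − p) = 1. Both arms take the covariate distribution of the whole population.
- Odds weights, 1 and p/(1 − p): rivaroxaban p × 1 = p; warfarin (1 − p) × p/(1 − p) = p. Both arms take the covariate distribution of the rivaroxaban patients.

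So (11) as worded standardises to everyone, which is the target of (7).

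**Size, by illustration**

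The Protocol gives no figure to reproduce. The preliminary counts since approval in section 9.b are 19,710 with a rivaroxaban claim and 48,380 with a warfarin claim, so the rivaroxaban share is 19,710/(19,710 + 48,380) = 19,710/68,090 = 28.9%. All other inputs are assumptions: one binary covariate with 50% prevalence, p = 0.42 and 0.16 in its two strata (mean 0.29), warfarin hazards 0.015 and 0.04 per year, and follow-up 2.5 years as in Table 1.

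Write HR₀ and HR₁ for the hazard ratios in the two strata. At the start of follow-up the marginal hazard ratios are:

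- Total population: (0.015·HR₀ + 0.04·HR₁)/(0.015 + 0.04)
- Treated: (0.42·0.015·HR₀ + 0.16·0.04·HR₁)/(0.42·0.015 + 0.16·0.04)

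For HR₀ = 0.70 and HR₁ = 0.95:

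- Total population: (0.0105 + 0.0380)/0.055 = 0.882
- Treated: (0.00441 + 0.00608)/0.0127 = 0.826

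Weighted Cox fits to 4,000,000 simulated patients with known p, beside the values from simulating both treatments for every patient, gave:

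| HR₀ / HR₁ | Cox, inverse probability weights | True, total population | Cox, odds weights | True, treated |
|---|---|---|---|---|
| 0.80 / 0.80 | 0.798 | 0.801 | 0.802 | 0.799 |
| 0.70 / 0.95 | 0.878 | 0.880 | 0.821 | 0.821 |
| 0.60 / 1.10 | 0.955 | 0.957 | 0.841 | 0.833 |
| 0.95 / 0.70 | 0.762 | 0.769 | 0.821 | 0.820 |

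In each scenario the inverse probability weights recover the total-population value and the odds weights the value in the treated, to within 0.01.

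A second set of runs (n = 2,000,000, 28.9% treated, hazard 2% per year) used a continuous risk score. The log hazard ratio changed by 0.1 to 0.3 per SD and the propensity slope was 0.5 to 1.0 per SD. Inverse probability versus odds weights ranged from 0.859 versus 0.826 (ratio 1.04) to 0.950 versus 0.777 (ratio 1.22).

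**The case against.** The strongest reply is that odds weighting is a member of the inverse probability family. The methods note treats it that way, so (11) may simply use the family name and leave the row heading to fix the target. Rows (9) and (22) show what the authors meant. They plainly know the issue, since they warn twice about comparing matching with weighting and restrict comparisons to a shared target. The entry is then a drafting slip that a careful analyst would not code literally, and the Protocol defers full implementation detail to a later document.

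It probably is a slip. But the family-name reading does not fit Table 3, which uses the two terms to separate target populations: inverse probability in (3), (7) and (17), inverse odds in (9) and (22). Nothing in the document says (11) uses odds weights. This is also not a detail left for later, because a weight is stated and it conflicts with its own row. Section 2.b says the study protocol will be generated from this proposal, so the wording can carry forward. The text damage in the PDF affects the row around (10), not the wording of (11).

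Several limits on scope and size do stand:

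- Only the hazard-ratio scale is affected. Approach (9) already gives an odds-weighted survival difference in the treated, and (7) is sound. Approach (11) is one of 25 and is not named as primary.
- Matching within calipers targets the treated only approximately, so (10) and a corrected (11) need not agree exactly.
- The 28.9% share comes from raw counts of people with at least one claim, before new-user and eligibility rules, and one person may appear in both counts.
- The upper ratio of 1.22 needs strong effect modification. A change of 0.3 per SD in the log hazard ratio is a factor of exp(1.2) = 3.3 across ±2 SD, combined with a steep propensity slope on the same score. Nothing in the Protocol supports or excludes this.

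**Conclusion.** The concern holds. As written, approach (11) estimates the hazard ratio in the total eligible population, not in the treated. It therefore repeats (7) and does not share a target with (10), which breaks the Protocol's own condition for comparing estimators. This follows from the wording of the table and the methods note and needs no numerical assumption.

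The numerical consequence cannot be derived from the documents. It is nil if the effect is homogeneous. If the effect varies with covariates that drive the choice of drug, the two hazard ratios separate, in either direction: by about 0.06 to 0.11 in the binary-covariate illustration, and by a ratio of 1.04 to 1.22 in the continuous-score one. These figures rest on assumed hazards, propensities and effect modification and show only that the gap can be material. Because the error sits in the table that decides which estimates may be compared, it should be corrected before analysis.

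**What to change.** In Table 3, keep the marginal structural Cox model in approach (11) but give it the weighting used in (9): "in the total study sample); inverse odds of treatment weighting". State the weights so that their direction is not in doubt: 1 for rivaroxaban patients and p/(1 − p) for warfarin patients, with p the estimated probability of rivaroxaban. Row (11) then agrees with (9), (22) and the methods note, and can be compared with (10).

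If the authors did intend inverse probability weights, (11) should be deleted as a repeat of (7). The hazard ratio in the treated would then rest on matching alone, so the first option is better.

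The cost is one phrase in the table and one weight definition in the code. No extra data are needed, and there is no statistical downside.
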